11.0 ADVERSE EVENT REPORTING

11.1 Leukemia-specific Adverse Event Recording and Reporting Guidelines

These guidelines serve to bring the Department of Leukemia in compliance with the institutional policy on Reporting of Serious Adverse Events.

Adverse event is any untoward medical occurrence that may present during treatment with a pharmaceutical product but which does not necessarily have a causal relationship with this treatment. Adverse drug reaction is a response to a drug which is noxious and unintended and which occurs at doses normally used in man for prophylaxis, diagnosis, or therapy of disease or for the modification of physiologic function.

Assessing causal connections between agents and disease is fundamental to the understanding of adverse drug reactions. In general, a drug may be considered a contributory cause of an adverse event if, had the drug not been administered, 1) the event would not have happened at all, 2) the event would have occurred later than it actually did, or 3) the event would have been less severe.

The Investigator or physician designee is responsible for verifying and providing source documentation for all adverse events and assigning the attribution for each event for all patients enrolled on the trial.

11.1.1 PDMS/CORe will be used as the electronic case report form for this protocol. Adverse events will be documented in the medical record and entered into PDMS/CORe.

11.1.2 These guidelines will be followed for the recording and reporting of adverse and serious adverse events.

- a. Baseline events will be recorded in the medical history section of the case report form and will include the terminology event name, grade, and start date of the event.
 - i. Baseline events are any medical condition, symptom, or clinically significant lab abnormality present before the informed consent is signed
 - a. Hematologic laboratory abnormalities will not be recorded as baseline events for patients with acute leukemia, myelodysplastic

- syndrome, chronic lymphocytic leukemia, or chronic myeloid leukemia in blast phase.
- b. If exact start date is unknown, month and year or year may be used as the start date of the baseline event.
- b. The maximum grade of the adverse event will be captured per course or protocol defined visit date.
- c. These adverse events will be recorded in the case report form:
 - i. Any grade adverse event that is possibly, probably, or definitely related to the study drug(s).
 - ii. All serious adverse events regardless of attribution to the study drug(s).
 - iii. Any grade adverse event regardless of attribution to the study drug(s) that results in any dose modification.
- d. Hematologic adverse events will not be recorded or reported for studies in patients with acute leukemia, myelodysplastic syndrome, chronic lymphocytic leukemia, or chronic myeloid leukemia in blast phase except for:
 - i. Prolonged myelosuppression as defined by the NCI-CTCAE criteria specific for leukemia, e.g. marrow hypocellularity on day 42 or later (6 weeks) from start of therapy without evidence of leukemia (< 5% blasts), or that results in dose modifications, interruptions or meets the protocol definition of DLT or SAE.
 - e. Serious adverse events will be reported according to institutional policy.
 - f. Protocol specific language regarding the recording and reporting of adverse and serious adverse events will be followed in the event of discordance between the protocol and Leukemia-specific adverse event recording and reporting guidelines.

11.1.3 Abnormal hematologic values will not be recorded on the case report form. For abnormal chemical values, the apogee or nadir (whichever is appropriate) will be reported per course on the case report form.

11.1.4 All events that are not listed as expected in section 11.1.2 will be collected for the purpose of grading, and determining attribution to study drugs by the PI using the following scale:

Unrelated: The AE is clearly NOT related to the intervention.

Unlikely: The AE is doubtfully related to the intervention.

Possible: The AE may be related to the intervention.

Probable: The AE is likely related to the intervention.

Definite: The AE is clearly related to the intervention.

11.1.5 All grade 3 and greater non-hematological events that are felt to be related to protocol treatment drugs will be documented on the toxicity log and entered into the case report form. The toxicity log and case report form data must reflect relationship to the drug the event is felt to be related to.

11.1.6 Serious Adverse Event Reporting (SAE)

An adverse event or suspected adverse reaction is considered “serious” if, in the view of either the investigator or the sponsor, it results in any of the following outcomes:

- Death
- A life-threatening adverse drug experience – any adverse experience that places the patient, in the view of the initial reporter, at immediate risk of death from the adverse experience as it occurred. It does not include an adverse experience that, had it occurred in a more severe form, might have caused death.
- Inpatient hospitalization or prolongation of existing hospitalization.
- A persistent or significant incapacity or substantial disruption of the ability to conduct normal life functions.
- A congenital anomaly/birth defect.

Important medical events that may not result in death, be life-threatening, or require hospitalization may be considered a serious adverse drug experience when, based upon appropriate medical judgment, they may jeopardize the patient or subject and may require medical or surgical intervention to prevent one of the outcomes listed in this definition. Examples of such medical events include allergic bronchospasm requiring intensive treatment in an emergency room or at home, blood dyscrasias or convulsions that do not result in inpatient hospitalization, or the development of drug dependency or drug abuse (21 CFR 312.32). Pregnancy, drug overdose, and secondary malignancy will be handled as SAE.

- Important medical events as defined above, may also be considered serious adverse events. Any important medical event can and should be reported as an SAE if deemed appropriate by the Principal Investigator or the IND Sponsor, IND Office.
- All events occurring during the conduct of a protocol and meeting the definition of a SAE must be reported to the IRB in accordance with the timeframes and procedures outlined in "The University of Texas M. D. Anderson Cancer Center Institutional Review Board Policy for Investigators on Reporting Unanticipated Adverse Events for Drugs and Devices". Unless stated otherwise in the protocol, all SAEs, expected or unexpected, must be reported to the IND Office, regardless of attribution (within 5 working days of knowledge of the event).

"Serious Adverse Event Reporting (SAE) for M. D. Anderson-Sponsored IND Protocols":

- All life-threatening or fatal events, that are unexpected, and related to the study drug, must have a written report submitted within 24 hours (next working day) of knowledge of the event to the Safety Project Manager in the IND Office.
- Unless otherwise noted, the electronic SAE application (eSAE) will be utilized for safety reporting to the IND Office and MDACC IRB.
- Serious adverse events will be captured from the time of the first protocol-specific intervention, until 30 days after the last dose of drug, unless the participant withdraws consent. Serious adverse events must be followed until clinical recovery is complete and laboratory tests have returned to baseline, progression of the event has stabilized, or there has been acceptable resolution of the event.
- Additionally, any serious adverse events that occur after the 100 day time period that are related to the study treatment must be reported to the IND Office. This may include the development of a secondary malignancy.

Reporting to FDA:

- Serious adverse events will be forwarded to FDA by the IND Sponsor (Safety Project Manager IND Office) according to 21 CFR 312.32.

It is the responsibility of the PI and the research team to ensure serious adverse events are reported according to the Code of Federal Regulations, Good Clinical Practices, the protocol guidelines, the sponsor's guidelines, and Institutional Review Board policy.

Investigator Communication with Supporting Companies:

- Any individual expedited SAE reports required by the FDA will be reported to BMS.
- **All Serious Adverse Events must be reported to BMS Worldwide Safety**
 - All SAEs, whether related or unrelated to nivolumab and all pregnancies must be reported to BMS (by the investigator or designee) within 48 hours.
 - All SAEs should be reported via confirmed facsimile (fax) transmission, or scanned and reported via electronic mail to:

SAE Email Address: [contact]

SAE [contact]

12.0 DISCONTINUATION OF STUDY TREATMENT

A patient's treatment with study drugs may be discontinued for any of the following reasons:

- Clinically significant progressive disease
- Adverse events that are not manageable with dose adjustments and/or optimal medical management, or that, in the opinion of the investigator, pose an unacceptable risk for the patient.
- Investigator decision
- Patient decision (e.g., withdrawal of consent)
- Study termination by Sponsor

Patients who experience toxicity that can be clearly attributed to either nivolumab or to ibrutinib may continue treatment with the other agent. If toxicity cannot be clearly attributed to a single agent, treatment with both agents should be discontinued. Patients who discontinue treatment for reasons other than progressive disease should remain on study and continue to have disease assessments per protocol.

Additional Discontinuation Criteria for Nivolumab

Treatment should be permanently discontinued for the following:

- Any Grade 2 drug-related uveitis or eye pain or blurred vision that does not respond to topical therapy and does not improve to Grade 1 severity within the re-treatment period OR requires systemic treatment
- Any Grade 3 non-skin, drug-related adverse event lasting > 7 days, with the following exceptions for drug-related laboratory abnormalities, uveitis, pneumonitis, bronchospasm, diarrhea, colitis, neurologic adverse event, hypersensitivity reactions, and infusion reactions

- Grade 3 drug-related uveitis, pneumonitis, bronchospasm, diarrhea, colitis, neurologic adverse event, hypersensitivity reaction, or infusion reaction of any duration requires discontinuation
- Grade 3 drug-related laboratory abnormalities do not require treatment discontinuation except those noted below:
 - Grade 3 drug-related thrombocytopenia > 7 days or associated with bleeding requires discontinuation
 - Any drug-related liver function test (LFT) abnormality that meets the following criteria require discontinuation:
 - AST or ALT > 8 x ULN
 - Total bilirubin > 5 x ULN
 - Concurrent AST or ALT > 3 x ULN and total bilirubin > 2 x ULN
- Any Grade 4 drug-related adverse event or laboratory abnormality, except for the following events which do not require discontinuation:
 - Isolated Grade 4 amylase or lipase abnormalities that are not associated with symptoms or clinical manifestations of pancreatitis and decrease to < Grade 4 within 1 week of onset.
 - Isolated Grade 4 electrolyte imbalances/abnormalities that are not associated with clinical sequelae and are corrected with supplementation/appropriate management within 72 hours of their onset
- Any dosing interruption lasting > 6 weeks with the following exceptions:
 - Dosing interruptions to allow for prolonged steroid tapers to manage drug-related adverse events are allowed. Prior to re-initiating treatment in a subject with a dosing interruption lasting > 6 weeks, the Investigator must be consulted. Tumor assessments should continue as per protocol even if dosing is interrupted
 - Dosing interruptions > 6 weeks that occur for non-drug-related reasons may be allowed if approved by the Investigator. Prior to re-initiating treatment in a subject with a dosing interruption lasting > 6 weeks, the Investigator must be consulted. Tumor assessments should continue as per protocol even if dosing is interrupted
- Any adverse event, laboratory abnormality, or intercurrent illness which, in the judgment of the Investigator, presents a substantial clinical risk to the subject with continued nivolumab dosing

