6.1.4 Endocrine adverse events

Endocrinopathies have been observed following treatment with nivolumab. Most cases are low or moderate grade. The events have typically been identified through either routine periodic monitoring of specific laboratories (eg, TSH) or as part of a work-up for associated symptoms (eg, fatigue). Events may occur within weeks of beginning treatment but also have been noted to occur after many months (while still on treatment). More than one endocrine organ may be involved. Early recognition and treatment of endocrinopathies are critical to its management. Patients should be advised to seek medical evaluation if they notice new onset of fatigue, lightheadedness, or difficulty with vision or if baseline fatigue worsens. As fatigue is common in patients with CLL, it is important that an evaluation/work-up distinguish between non-drug- related causes (eg, progression of disease, anemia, concomitant medications, depression) and a possible drug-related AE as the management is quite different. The principal management of endocrinopathies is hormone replacement therapy.

Asymptomatic TSH elevation	
 Continue nivolumab If TSH < 0.5 x LLN, or TSH > 2 x ULN, or consistently out of range in 2 subsequent measurements: consider endocrinology consult 	
Symptomatic endocrinopathy	
 Evaluate endocrine function Consider pituitary scan 
Symptomatic with abnormal lab/pituitary scan:
 
 Delay nivolumab Steroids: 1-2 mg/kg/day methylprednisolone IV or PO equivalent Initiate appropriate hormone therapy 
No abnormal lab/pituitary MRI scan but symptoms persist:
 
 Repeat labs in 1-3 weeks / MRI in 1 month 	
If improves (with or without hormone replacement):
 
 Taper steroids over at least 1 month and consider prophylactic antibiotics for opportunistic infections Resume nivolumab Patients with adrenal insufficiency may need to continue steroids with mineralocorticoid component
Suspicion of adrenal crisis (e.g. severe dehydration, hypotension, shock out of proportion to current illness)	
 Delay or discontinue nivolumab Rule out sepsis Stress dose of IV steroids with mineralocorticoid activity IV fluids Consult endocrinologist If adrenal crisis ruled out, then treat as above for symptomatic endocrinopathy 	

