6.1.7 Neurologic adverse events

Neurologic AEs have been uncommonly observed following treatment with nivolumab. Neurologic AEs can manifest as central abnormalities (eg, aseptic meningitis, encephalitis) or peripheral sensory/motor neuropathies (eg, Guillain-Barre Syndrome). Early recognition and treatment of neurologic AEs is critical to its management. Patients should be advised to seek medical evaluation if they notice impairment in motor function (eg, weakness), changes in sensation (eg, numbness), or symptoms suggestive of possible central nervous system abnormalities such as new headache or mental status changes. As neurologic symptoms can be common in patients with cancer, it is important that an evaluation/work-up distinguish between non-drug-related causes (eg, progression of disease, concomitant medications, infection) and a possible drug-related AE as the management is quite different.

Grade of Neurological Toxicity	Management	Follow-up
Grade 1 (Asymptomatic or mild symptoms; intervention not indicated)	
 ▪ Continue nivolumab 	
 ▪ Continue to monitor patient If worsens: 
 ▪ Treat as Grade 2 or 3-4
Grade 2 (Moderate symptoms; limiting instrumental ADL)	
 ▪ Delay nivolumab ▪ Symptomatic treatment ▪ Steroids: 0.5-1 mg/kg/day methylprednisolone IV or oral equivalent 	If improves to baseline: 
 ▪ Resume nivolumab If worsens: 
 ▪ Treat as Grade 3-4
Grade 3-4 (Severe symptoms; limiting self-care ADL; life-threatening)	
 ▪ Discontinue Nivolumab ▪ Neurology consult ▪ Symptomatic treatment ▪ Steroids: 1-2 mg/kg/day methylprednisolone IV or IV equivalent ▪ Add prophylactic antibiotics for opportunistic infections 	If improves to Grade 2: 
 ▪ Taper steroids over at least 1 month If worsens or atypical presentation: 
 ▪ Consider IVIG or other immunosuppressive therapies

Patients on IV steroids may be switched to an equivalent dose of oral corticosteroids (e.g. prednisone) at start of tapering or earlier, once sustained clinical improvement is observed.

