6.1.11 Criteria to Resume Treatment

Patients may resume treatment with study drug when the drug-related AE(s) resolve to Grade ≤1 or baseline value, with the following exceptions:

- Patients may resume treatment in the presence of Grade 2 fatigue
- Patients who have not experienced a Grade 3 drug-related skin AE may resume treatment in the presence of Grade 2 skin toxicity
- Patients with baseline Grade 1 AST/ALT or total bilirubin who require dose delays for reasons other than a 2-grade shift in AST/ALT or total bilirubin may resume treatment in the presence of Grade 2 AST/ALT OR total bilirubin
- Patients with combined Grade 2 AST/ALT AND total bilirubin values meeting discontinuation parameters (Discontinuation Section, Section 12.0) should have treatment permanently discontinued
- Drug-related pulmonary toxicity, diarrhea, or colitis, must have resolved to baseline before treatment is resumed
- Drug-related endocrinopathies adequately controlled with only physiologic hormone replacement may resume treatment

If the criteria to resume treatment are met, the subject should restart treatment at the next scheduled timepoint per protocol. However, if the treatment is delayed past the next scheduled timepoint per protocol, the next scheduled timepoint will be delayed until dosing resumes.

If treatment is delayed > 6 weeks, the subject must be permanently discontinued from study therapy, except as specified in discontinuation section.

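### Section 12.0 permanently stops nivolumab after a Grade 3 endocrinopathy lasting more than 7 days or a Grade 4 one, while 6.1.4 and 6.1.11 let it resume, and no section is said to govern

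*Combined protocol and SAP*

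**What the plan says.** **Section 12.0, additional criteria for nivolumab.** Treatment should be permanently discontinued for "Any Grade 3 non-skin, drug-related adverse event lasting > 7 days". This rule carries a list of exempted conditions, which reads in full: "with the following exceptions for drug-related laboratory abnormalities, uveitis, pneumonitis, bronchospasm, diarrhea, colitis, neurologic adverse event, hypersensitivity reactions, and infusion reactions". Most of the excepted conditions are then given their own, stricter rule, and Grade 3 laboratory abnormalities are largely released from the requirement. Endocrinopathy is not on the list. The next rule stops nivolumab for "Any Grade 4 drug-related adverse event or laboratory abnormality, except for the following events which do not require discontinuation". Only two exceptions follow. One is "Isolated Grade 4 amylase or lipase abnormalities that are not associated with symptoms or clinical manifestations of pancreatitis" that fall below Grade 4 within a week; the other is isolated electrolyte abnormalities corrected within 72 hours. Neither is an endocrinopathy.

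**Section 6.1.4.** For a symptomatic endocrinopathy with an abnormal laboratory value or pituitary scan, the table delays nivolumab and gives steroids and hormone therapy. If the event improves, with or without hormone replacement, it tapers the steroids and resumes nivolumab. The rows are not graded.

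**Section 6.1.11.** Among the exceptions to the general threshold for resuming: "Drug-related endocrinopathies adequately controlled with only physiologic hormone replacement may resume treatment".

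**Section 6.0.** Grade 3 or 4 immune-related toxicity from nivolumab will generally lead to its discontinuation, with ibrutinib continuing alone.

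**Neurologic events.** The Grade 2 row of 6.1.7 resumes nivolumab under the condition "If improves to baseline". The general rule of 6.1.11 is Grade 1 or lower, or baseline. Its stricter baseline-only exception reads "Drug-related pulmonary toxicity, diarrhea, or colitis, must have resolved to baseline before treatment is resumed" and does not name neurologic events.

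**The concern.** A site treating a patient whose severe endocrinopathy has improved must decide whether nivolumab is finished or may restart. Section 12.0 answers that it is finished. Sections 6.1.4 and 6.1.11 answer that it may restart. Re-treatment after a severe drug-related event is a safety decision, and the protocol should give one answer to it.

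The gap is easy to miss because the endocrine table differs from most of its neighbours. The tables for pneumonitis, diarrhea/colitis, hepatic, renal and neurologic events each contain a grade at which nivolumab is discontinued. The endocrine table contains none, so someone working from it would not be prompted to look at Section 12.0. How many patients are recorded as discontinued, and how much nivolumab they receive, would then depend partly on which section was consulted.

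**Working it through.** The plan gives no figure to reproduce here. The check is a comparison of text, followed by a short calculation of how many patients it could touch.

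**Step 1. One patient, each section in turn.** Take a symptomatic, drug-related endocrinopathy that later improves and is adequately controlled on physiologic hormone replacement alone.

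| Worst grade and duration | Section 12.0 | 6.1.4 | 6.1.11 | 6.0 |
|---|---|---|---|---|
| Grade 3, more than 7 days | Permanent stop (non-skin, no exception applies) | Resume | May resume | Generally stop |
| Grade 4, any duration | Permanent stop (neither exception applies) | Resume | May resume | Generally stop |
| Grade 3, 7 days or less | No stop under this rule | Resume | May resume | Generally stop |
| Grade 2 | No stop under this rule | Resume | May resume | Not addressed |

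The first two rows are the contradiction between Section 12.0 and Sections 6.1.4 and 6.1.11.

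Two boundaries apply. Section 12.0 catches endocrinopathy through its general wording and the absence of an exception, not by name. Grade 3 findings that are only laboratory abnormalities are exempt there, so the Grade 3 conflict concerns clinical endocrinopathy.

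**Step 2. Is precedence stated?** Section 6.1.11 points to the discontinuation section in two places: combined AST/ALT and bilirubin values, and delays of more than 6 weeks. Its endocrine item has no such pointer, and neither does 6.1.4. Section 6.0 adds a third, softer wording. No section says which prevails.

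**Step 3. How many patients?** The inputs come from Table 2.4.2.4-1 (treatment-related select adverse events, nivolumab alone) and from the maximum of 72 patients in Section 14.0.

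- Grade 3-4 endocrinopathy, all doses: 3/306. Scaled to this trial: 72 × 3/306 = 0.7 patients.
- All three were at 10 mg/kg. At the doses up to 3 mg/kg the count is 0 of 17 + 18 + 86 + 54 = 175.
- At 3 mg/kg, the dose used here: 0/54. The exact one-sided 95% upper bound for zero events is 1 − 0.05^(1/54) = 0.054, or 5.4%. Scaled: 72 × 0.054 = 3.9, about 4 patients.

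The dose-matched estimate is therefore zero, and the data are compatible with up to about 4 of 72. Even that overstates the conflict, because a Grade 3 event must also last more than 7 days and be clinical. The documents give no rate for the combination with ibrutinib.

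**Step 4. Neurologic events.** Take a Grade 2 event that improves to Grade 1 in a patient with no such symptom at baseline. It meets the general threshold of 6.1.11 but not the baseline threshold of 6.1.7. Neither section ends nivolumab permanently for this patient. For Grade 3-4 neurologic events, 6.1.7 and Section 12.0 both discontinue.

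**The case against.** The best defence is that the sections form a sequence: 6.1.10 says when to delay, 6.1.11 when to resume, and Section 12.0 when to stop for good. On that reading the endocrine item in 6.1.11 relaxes only the threshold for resuming. It is permissive, while Section 12.0 is directive, and 6.0 already leans towards stopping. This is a coherent reading, and many investigators would adopt it. But the text does not state it. Section 6.1.4 gives resumption as the follow-up step without limit of grade, and cross-references appear elsewhere in 6.1.11 but not on the endocrine item.

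A reader might also infer more than the documents support:

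- *That the adrenal-crisis row contradicts Section 12.0.* That row concerns a suspected crisis and offers delay or discontinuation. A site can delay during the work-up and discontinue if a drug-related Grade 4 event is confirmed, which satisfies both. The documents do not grade adrenal crisis.
- *That the month-long steroid taper in 6.1.4 breaches the 7-day rule.* Section 12.0 counts the duration of the Grade 3 event, not of the taper, and it expressly allows interruptions for prolonged tapers.
- *That neurologic patients get opposite instructions on permanent discontinuation.* They do not. Only the moment of resuming differs, and a site that waits for baseline satisfies both sections.
- *That the any-grade rate of 29/306 measures the problem.* Grade 1-2 endocrinopathy is not in conflict.
- *That the efficacy conclusion is threatened.* Section 14.0 sets no endpoint on discontinuation or exposure, all nivolumab is given at one centre, and patients who stop for reasons other than progression stay on study with disease assessments. No effect on the primary endpoints has been shown.

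**Conclusion.** The contradiction stands for one defined group: patients with a clinical, drug-related endocrinopathy that is Grade 3 for more than 7 days, or Grade 4, and then improves. For them the protocol gives both permanent discontinuation and resumption, and no rule of precedence settles it.

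The group is likely to be small: none expected from the dose-matched data, with an upper bound of about 4 of 72. This assumes that nivolumab-alone rates from a study in advanced solid tumors carry over to CLL and Richter transformation treated together with ibrutinib, which the documents cannot confirm. The point rests on patient safety and consistent conduct, not on the trial's power or error rates. It should be corrected, because each affected patient faces a decision on re-treatment after a severe event. The Grade 2 neurologic mismatch is real but minor.

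**What to change.** Reconcile Section 12.0 with 6.1.4, 6.1.11 and 6.0 for endocrinopathy that is Grade 3 for more than 7 days or Grade 4, so that all four give the same instruction. Reconcile 6.1.7 with 6.1.11 on the threshold for resuming after a Grade 2 neurologic event. Add one sentence stating which section governs where the organ tables, the resume criteria and the discontinuation criteria differ, and put a cross-reference to Section 12.0 in 6.1.4 and on the endocrine item of 6.1.11.

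Which clinical rule to adopt is for the sponsor to decide. The cost is an amendment of wording; sample size, visit schedule and analysis do not change.
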